# **11 STATISTICS AND ANALYSIS**

## 11.1 Sample size calculation

The largest study to date using ICMs was performed in 1049 patients with known AF which were followed for 3 months. AF episodes longer than 6 minutes were seen in 53% of patients who had, on average, 7 AF episodes per month. We will recruit patients with known high frequency of AF episodes therefore we can assume AF episodes in least 40% of patients during the 6 months study period. Using the Buderer's formula, 327 episodes of AF are required if the expected AF detection algorithm sensitivity is 95% and the specificity is 85% with a 95% confidence interval. Therefore, with a rate of 7 episodes per month a minimum of 8 subjects for each ICM is needed. We will aim to recruit 30 patients so that a broad spectrum of patient characteristics can be accounted for.

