# 5. 1 Hypothesis

Injectable and wearable technologies have huge potential to improve the management of patients with AF, both as a diagnostic tool but also to guide therapies. "As-needed" use of oral anticoagulants has been proposed as a cost-effective way to prevent thromboembolic stroke as well as increasing patient compliance and satisfaction. However, its utility is dependent on having very sensitive, reasonably specific detection of clinically relevant AF episodes and high transmission success. It is therefore important to determine how accurate the latest devices and their detection algorithms are when compared to the gold standard of CIEDs (pacemakers, implantable cardiac defibrillators (ICD) and cardiac resynchronisation therapy (CRT) devices) that have atrial leads and constant monitoring

We hypothesize that the new generation ICMs (Confirm Rx™ and Reveal LINQ™) can identify the majority (sensitivity above 95%, positive predictive value above 85%) of clinically significant AF episodes (longer than 6 minutes). We also estimate that with Bluetooth® technology connecting to patients' smartphone will improve the transmission success rate above 80%.

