# 7. STUDY DESIGN

The ID-AF study is a prospective, single centre, randomised observational study aimed at comparing the performance of the Confirm  $Rx^{M}$  and Reveal LINQM ICMs in the detection of clinically relevant atrial fibrillation (AF) episodes to cardiac implantable electronic devices (CIED)

Subjects with pre-existing cardiac implanted electronic devices (Pacemakers, CRT and ICD devices) who have remote monitoring ability and are able to record electrograms will be identified by interrogation of the John Radcliffe Hospital Pacemaker Database. Subjects with a functioning atrial lead, on remote monitoring, non-permanent AF with an AF burden of more >2% in the last year will be invited to participate. Those who have expressed an interest in participating will be invited for an initial interview (eligibility assessment, baseline assessment and informed consent).

[figure not shown]
This study will randomise 30 subjects to receive either a Confirm Rx™ ICM or a Reveal LINQ™ ICM. The ICM will be implanted in the Outpatient setting as a Day Case Procedure according to manufacturer instructions. Prior to the implant, 2 minutes of recording in V1 and V2 position with the surface ICM mapping will be performed. The R-wave amplitude will be recorded at the end of the procedure. Subjects will be taught how to use the home-based transmitter and mobile app.

As it is standard of care, the research team will book a telephone follow-up appointment at 4-6 weeks to address any questions the subjects may have regarding the ICM, review ICM battery and wound. The ICMs are programmed for automatic daily transmissions of the recorded episodes to the Clinician's Web Portal. Scheduled remote transmissions for CIED will be performed at least monthly. At 6 months, subjects will be invited to attend a Device Clinic appointment for the final download from both devices. At this time, they may choose to have the ICM removed or left in-situ but turned off. During this last visit, ICM transmissions log will be interrogated. The end of the study for each patient will be the date of the 6 months follow-up appointment.

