## 8.8 Blinding

Investigators and subjects will not be blinded to investigation arm.

At the end of follow-up, the CIED and ICM electrograms catalogued by the devices as AF will be adjudicated by two electrophysiologists blinded to patient data.

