## 8.10 Subsequent Visits

# 8.10.1 Scheduled Remote ICM and CIED Transmissions

Scheduled monthly remote ICM and CIED transmissions will be performed. Electrograms catalogued as AF episodes by the both devices will be downloaded for analysis from the clinicians web portal where the data is safely stored in Medtronic™ and Abbott™ server as it standard practice. All transmissions will be anonymous and only identified by the trial ID number.

If due to technical difficulties remote download is not possible subjects will be invited to attend Pacemaker Clinic for a download.

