## 11.2 Analysis of Outcome measures

Descriptive statistics are reported as count and percentage for categorical variables and mean and standard deviation for continuous variables.

The ICM performance will be investigated by calculating the sensitivity, specificity, positive predictive value and negative predictive value of AF episodes longer than 6 minutes will be calculated

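### The minimum of 8 patients per ICM counts about 42 episodes per patient as independent and assumes every patient has episodes; section 11.2 names no interval and no unit for specificity or NPV

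*Combined protocol and SAP*

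**What the plan says.** Section 11.1 (Sample size calculation) states "Using the Buderer's formula, 327 episodes of AF are required", for an expected sensitivity of 95% and specificity of 85% with 95% confidence. It then concludes that "with a rate of 7 episodes per month a minimum of 8 subjects for each ICM is needed". The episode rate comes from a cited study in which 53% of patients had episodes longer than 6 minutes, at 7 per month on average. For its own patients the plan assumes AF episodes in at least 40%. The larger planned size has a separate reason: "We will aim to recruit 30 patients so that a broad spectrum of patient characteristics can be accounted for". The synopsis (section 3) puts 15 in each arm.

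Section 7 gives each patient one device: "This study will randomise 30 subjects to receive either a Confirm Rx" ICM or a Reveal LINQ ICM. Section 11.2 describes the primary analysis as "calculating the sensitivity, specificity, positive predictive value and negative predictive value of AF episodes longer than 6 minutes", and says nothing about intervals, repeated episodes in a patient, or what counts as a true negative.

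Two other sections describe the data that reach the analysis. Section 8.8 says that "the CIED and ICM electrograms catalogued by the devices as AF will be adjudicated", and section 8.10.1 that "Electrograms catalogued as AF episodes by the both devices will be downloaded for analysis". The hypothesis in section 5.1 is "sensitivity above 95%, positive predictive value above 85" per cent.

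**The concern.** All of a patient's episodes are sensed by one implant in one chest position, so detection errors may well cluster by patient. If they do, 42 episodes carry less information than 42 independent ones. Neither the sizing nor the analysis allows for this. The size of the correlation is unknown, and the signal may also drift within a patient, since R-wave change is a secondary objective.

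The sizing also divides by 42 as though every patient supplied episodes, which does not fit the 40% assumption in the same paragraph.

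Specificity and NPV need a count of non-AF units. Only electrograms labelled AF are downloaded and adjudicated, and no section divides the remaining monitored time into units. Two of the four primary measures therefore have no defined denominator.

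At stake is how precision is read against the 95% and 85% figures in section 5.1.

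**Working it through.** **Inputs.** From section 11.1: 7 episodes per month, 327 required, sensitivity 0.95, specificity 0.85, 40% of patients with AF. From section 7: 6 months of follow-up. From the synopsis: 15 patients per ICM. The PPV of 0.85 is the section 5.1 figure. Not in the documents: the half-width *d* (inferred below), the ICC (assumed 0 to 0.20), the variation in episode counts (coefficient of variation, CV, assumed 1.0 as an unequal case), and device detections per patient for PPV (assumed 42).

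**Reproducing 327.** The specificity form of Buderer's formula is z²·Sp(1−Sp)/[d²(1−prev)]. With d = 0.05 and prev = 0.40:

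1.96² × 0.85 × 0.15 / (0.05² × 0.60) = 326.5, which rounds up to 327.

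Of the half-widths tried (0.03, 0.04, 0.05, 0.07, 0.10, with prevalence 0.40 or 0.53), only this combination returns 327. So 327 is a total of AF and non-AF units, and the 40% of patients has been used as a prevalence of units. The sensitivity form gives 1.96² × 0.95 × 0.05 / 0.05² = 73.0 AF episodes (182.5 units in total at prevalence 0.40). For a PPV of 85% the same margin needs 1.96² × 0.85 × 0.15 / 0.05² = 195.9 detections.

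**Reproducing 8.** 7 × 6 = 42 episodes per patient; 327/42 = 7.79, so 8.

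**What the division assumes.** With 40% of patients contributing, 8 patients give 8 × 0.40 × 42 = 134 episodes and 15 give 15 × 0.40 × 42 = 252. Both are below 327 before any clustering.

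**Allowing for clustering.** The design effect is DE = 1 + (m − 1)·ICC with m = 42, so DE = 1 + 41·ICC. With unequal counts, DE = 1 + [(CV² + 1)m − 1]·ICC, which is 1 + 83·ICC at CV 1.0. The 95% half-width is 1.96·√[p(1−p)·DE/n], where n is the total number of episodes or detections.

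Half-width in points, sensitivity 95% / PPV 85%:

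| ICC | 15 patients, equal (n = 630) | 15 patients, CV 1.0 (n = 630) | 10 contributing (n = 420) | 6 contributing (n = 252) |
|---|---|---|---|---|
| 0 | 1.7 / 2.8 | 1.7 / 2.8 | 2.1 / 3.4 | 2.7 / 4.4 |
| 0.01 | 2.0 / 3.3 | 2.3 / 3.8 | 2.5 / 4.1 | 3.2 / 5.2 |
| 0.02 | 2.3 / 3.8 | 2.8 / 4.6 | 2.8 / 4.6 | 3.6 / 5.9 |
| 0.05 | 3.0 / 4.9 | 3.9 / 6.3 | 3.6 / 6.0 | 4.7 / 7.7 |
| 0.10 | 3.8 / 6.3 | 5.2 / 8.5 | 4.7 / 7.7 | 6.1 / 10.0 |
| 0.20 | 5.2 / 8.5 | 7.1 / 11.7 | 6.3 / 10.4 | 8.2 / 13.4 |

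The 10-patient column is an assumed middle case. The last two columns take equal counts among the patients who contribute.

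**Largest ICC at which ±5 points holds.** For equal counts this is (n/required − 1)/41; at CV 1.0 the divisor is 83.

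- 15 patients, equal counts: sensitivity (630/73.0 − 1)/41 = 0.19; PPV (630/195.9 − 1)/41 = 0.05.
- 15 patients, CV 1.0: sensitivity (630/73.0 − 1)/83 = 0.09; PPV (630/195.9 − 1)/83 = 0.03.
- 6 contributing: sensitivity (252/73.0 − 1)/41 = 0.06; PPV (252/195.9 − 1)/41 = 0.007.

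**If a pooled binomial interval were used.** In a beta-binomial simulation (15 patients with 42 episodes each, true sensitivity 95%, 20,000 runs per setting), a nominal 95% Wilson interval that ignored patients covered the truth in about 96 / 91 / 87 / 75 / 63 / 49% of runs at ICC 0 / 0.01 / 0.02 / 0.05 / 0.10 / 0.20.

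**The case against.** The plan recruits 15 per ICM, and 8 is only a floor. That stands: the extra patients absorb part of the problem, and if all 15 contribute 42 episodes, sensitivity keeps a ±5-point margin over most of the ICC range. But the reason given for 30 is patient spectrum, and enlarging the sample does not validate a pooled interval: the coverage figures above are for 15 patients.

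A reader might infer that 8 patients fail at almost any correlation, since 336 episodes fall below 327 effective ones once the ICC passes (336/327 − 1)/41 = 0.0007. That is too strong. The limit mostly reflects rounding 7.79 up to 8, and it uses 327 as an AF-episode target, which it is not. Against 73 AF episodes, 8 contributing patients hold to an ICC of about 0.09.

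A reader might equally infer that 15 patients are simply adequate. The documents do not support that either, because it needs every patient to contribute and the counts to be similar. The recruitment target of an AF burden above 2% (section 7) makes more than 40% contributing plausible, but the plan's own floor is 40%.

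Finally, this is a pilot that plans point estimates only. That also stands. The low coverage belongs to an interval the plan does not propose, so the harm is conditional.

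**Conclusion.** The point holds in a limited form and should be fixed. Three parts need no assumed ICC: the step from 327 to 8 has no allowance for repeated episodes or for patients without any, 327 is described as AF episodes when the formula makes it a total of AF and non-AF units, and specificity and NPV have no unit.

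The numerical effect is uncertain. It rests on an assumed ICC range, an inferred 5-point margin, and assumptions about who contributes and how unevenly. Across the cases shown, ±5 points holds up to an ICC between about 0.06 and 0.19 for sensitivity and between about 0.007 and 0.05 for PPV. The documents do not show that the study will report an invalid interval. They show that nothing prevents one, and that the sizing points towards pooling.

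**What to change.** **Section 11.1.** Describe 327 as the specificity-driven total of AF and non-AF units and state the half-width used. Replace the minimum of 8 with the precision expected from 15 patients per ICM over a stated ICC range (for example 0 to 0.20), including 6 and 10 contributing patients and unequal episode counts. Make no unconditional claim that 15 is adequate.

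**Section 11.2.**

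1. Name the AF episode as the unit for sensitivity and PPV.
2. Name a fixed-length monitoring window, classified by the CIED, as the unit for specificity and NPV. Before data review, fix its length, the rule for a window holding both detected and missed AF, and the retention of episode onset and offset logs. State that these two measures are on a different unit from sensitivity and PPV.
3. Report each measure per ICM with a 95% interval clustered on patient with a small-sample correction, for example GEE with a bias-corrected standard error. Use the same clustered approach for any device comparison.
4. Name one fallback interval for a device with no errors, for example an exact interval on the effective number of units (units divided by the design effect) at one pre-stated ICC.

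**Cost.** Wording and a standard model, with no change to recruitment. Clock synchronisation is already planned (section 8.9.1), but no section says that complete onset and offset logs will be kept, so this must be added. The intervals will be wider and, with about 15 patients, approximate: in simulation over ICC 0 to 0.20, bias-corrected GEE coverage at 95% sensitivity ran from about 96% down to 92% with equal counts, and from 95% down to 89% at CV 1.0.

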## 11.2 Analysis of Outcome measures

Descriptive statistics are reported as count and percentage for categorical variables and mean and standard deviation for continuous variables.

The ICM performance will be investigated by calculating the sensitivity, specificity, positive predictive value and negative predictive value of AF episodes longer than 6 minutes will be calculated

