# 3. SYNOPSIS

Trial Title	Comparison of the performance of Implantable Cardiac Monitors and Cardiac Implantable Electronic Devices in detecting Atrial Fibrillation				
Internal ref. no. (or short title)	ID-AF				
Trial registration	Intended register – Clinicalt	rials.gov			
Sponsor	Oxford University Hospitals	NHS Foundation Trust			
Funder	Cardiac Rhythm Research H Abbott Medical Medtronic	ub (Oxford University Hospital	s)		
Clinical Phase	Pilot study				
Trial Design	Prospective, single centre, r	andomised observational stud	ly.		
Trial Participants		ith a dual-chamber CIED with or Persistent Atrial Fibrillation	a functioning		
Sample Size	30 subjects (15 on each investigation arm)				
Planned Trial Period	15 months Extension of study end date until 30 th June 2024				
Planned Recruitment period	<del>3 – 6 months</del> Extension of recruitment period until 31 st December 2023				
	Objectives	Outcome Measures	Timepoint(s)		
Primary	Primary Objective 1. To compare the performance of the Confirm Rx ™ ICM and Reveal LINQ ™ ICM in detecting clinically significant AF episodes (episodes longer than 6 minutes) to CIED (gold standard).	1. Confirm Rx and Reveal LINQ ™ ICM sensitivity, specificity, positive predictive value and negative predictive value will be calculated for AF episodes longer than 6 minutes	During follow-up (6 months)		
Secondary	Secondary Objectives				
	1. To compare the changes in R-wave amplitude following implantation in both ICMs.	
 
Compared the percentage of changes in R-wave amplitude between both ICMs
 
	1. During the follow- up period (6 month)		
	2. To compare the transmission success rate	
 
The percentage of successful transmission in both ICMs will be calculated.
 
	2. During the follow- up period (6 month)		

	of both devices. 3. To compare between both devices the number of patient- activated recordings that contains symptoms attributed to those episodes.	3. The percentage of activated recordings with symptoms will be calculated.	3. During follow-up period (6 months)
Intervention(s) 
 
Medical Device
 
	Implantable cardiac monito LINQ™(Medtronic)	ors (ICM): Confirm Rx™ (Abbo	tt) and Reveal
Comparator		ectronic Devices (Pacemak Implantable cardioverter-defi	

|

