First generation implantable cardiac monitors (ICM) were implanted subcutaneously, using blunt dissection, in the catherisation laboratory. Their AF detection algorithm was rudimentary, relying solely on irregular R-R intervals measurements. As a result, they were prone to false positive results caused by artefact and other irregular rhythms such as ventricular ectopy. The SMJ Confirm™ ICM had a sensitivity of 94% but a positive predictive value of only 64% for detection of clinically significant AF episodes (longer than 6 minutes). Furthermore, all ICMs transmissions to the Clinician's Web Portal required the subject to be within 2 metres of the home transmitter which resulted in suboptimal transmission success.

New generation Implantable cardiac monitors (ICM): They offer a minimally invasive approach for continuous ECG monitoring. ICMs outperform the external ambulatory ECG in the diagnosis of clinically significant arrhythmias in patients presenting with palpitations, syncope, cryptogenic stroke and post-AF ablation. . AF detection relies on a two-step approach. Firstly, they identify irregular R-R intervals and either a Markov chain model or Lorenzo plot to assign an AF probability score. Secondly, they review

the electrograms for any evidence of P waves. If no P waves are detected it is logged as AF. The two ICM to be studied are:

Reveal LINQTM ICM (MedtronicTM): Commonly used ICM with reported high sensitivity and positive predicted value. However, its AF algorithm has never been validated against CIED. Transmissions are performed through a home-monitor, 20% of which are unsuccessful I[4]. The most current version can use a smartphone app (MedtronicTM) and Bluetooth® connection to transmit the recording, however the transmission success rate has not been studied.

Confirm RxTM ICM X (AbbottTM): Was the first ICM equipped with Bluetooth® wireless technology that connects directly with the patient's smartphone via the myMerlinTM app (AbbottTM). The myMerlinTM app features include activation of ECG recordings when experiencing symptoms, viewing of transmission history to confirm successful data transfer and receiving notifications for scheduled transmission and device checks. Neither the AF algorithm nor the myMerlin App have been independently validated.

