# 6. OBJECTIVES AND OUTCOME MEASURES

Objectives	Outcome Measures	Timepoint(s) of evaluation of this outcome measure (if applicable)
Primary Objective 1. To compare the performance of the Confirm Rx ™ ICM and Reveal LINQ ™ ICM in detecting clinically significant AF episodes (episodes longer than 6 minutes) to cardiac implantable electronic devices (CIED).	1. Confirm Rx and Reveal LINQ ™ ICM sensitivity, specificity, positive predictive value and negative predictive value will be calculated for AF episodes longer than 6 minutes	During follow-up (6 months)
Secondary Objectives		
1. To compare changes in the recording of electrograms (heart's electrical activity) R- wave amplitude from time of implant to end of follow-up (6 months)	
 
Compared the percentage of changes in R-wave amplitude between both ICMs
 
	1. During the follow- up period (6 month)
2. To compare the transmission success rate of episodes recorded by the implantable cardiac monitors to the Clinician's Web Portal.	2. The percentage of successful transmission in both ICMs will be calculated.	2. During the follow- up period (6 month)
3. To compare between both devices the number of patient-activated recordings that contains symptoms \\cts attributed to those episodes	3. The percentage of activated recordings with symptoms will be calculated.	3. During follow-up period (6 months)
Exploratory Objectives		
1. To study the changes in P-wave amplitude between different positions in the chest.	1. Percentage of change in P and R- wave amplitudes between V1 and V2 position. Percentage of change in P and R-wave amplitudes between surface	1. During implant

Trial Protocol	Version 1. 2 4 /Date: 0326/087/20234
ID-AF Study	IRAS Project number: 268739
Chief Investigator: [name]	- REC Ref: 21/LO/0508 ←
	Page 12 of 28

| |

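### The 327 in section 11.1 is a total of AF and non-AF units, not a number of AF episodes, and specificity and NPV have no defined non-AF unit

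*Combined protocol and SAP*

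**What the plan says.** The primary outcome in section 6 (and in the section 3 synopsis) is that Confirm Rx and Reveal LINQ "ICM sensitivity, specificity, positive predictive value and negative predictive value will be calculated for AF episodes longer than 6 minutes". Section 11.2 repeats that the "sensitivity, specificity, positive predictive value and negative predictive value of AF episodes longer than 6 minutes will be calculated" and gives no counting unit and no two-by-two table.

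Section 11.1 uses Buderer's formula and states that "327 episodes of AF are required if the expected AF detection algorithm sensitivity is 95% and the specificity is 85"%, with a 95% confidence interval. It gives no half-width. Just before that it says "we can assume AF episodes in least 40% of patients during the 6 months study period". It then concludes that "with a rate of 7 episodes per month a minimum of 8 subjects for each ICM is needed". The planned total is 30 patients, 15 per ICM, chosen to cover a broad range of patient characteristics.

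Section 5.1 sets accuracy targets for two measures only: "sensitivity above 95%, positive predictive value above 85"%. Specificity and NPV have no target.

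**The concern.** Specificity is TN/(TN+FP) and NPV is TN/(TN+FN). Both need a count of true negatives, so some unit must be able to be free of AF. An AF episode cannot be that unit. If the unit is chosen after the data are seen, the reported level of two of the four primary measures follows from that choice. Investigators are not blinded to arm (section 8.8).

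Buderer's formula also needs units with and without the condition, and a prevalence among those units. Section 11.1 reports the result as AF episodes only, converts it to patients with the AF episode rate, and takes its prevalence from a share of patients. A reader therefore cannot tell how many AF episodes are needed, or whether 15 patients per ICM supply them.

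**Working it through.** **Inputs.** From section 11.1: sensitivity 0.95, specificity 0.85, 95% confidence (z = 1.96), 40% of patients with episodes, 7 episodes per month. Follow-up is 6 months, so a patient with episodes contributes 7 × 6 = 42. From section 3: 15 patients per ICM. The half-width d is not in the documents.

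**Reproducing 327.**
- Specificity: 1.96² × 0.85 × 0.15 / 0.05² = 195.9 non-AF units. Dividing by 1 − 0.40 gives 326.5, rounded up to **327 units in total**.
- Split: 0.40 × 327 = 130.8 AF units and 0.60 × 327 = 196.2 non-AF units.
- Sensitivity: 1.96² × 0.95 × 0.05 / 0.05² = 73.0 AF units. Dividing by 0.40 gives 182.5, rounded up to 183 in total.

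Both forms were tried with d = 0.03, 0.04, 0.05, 0.06, 0.07 and 0.10, prevalence 40% and 53% (the share in the cited study), and one- and two-sided z. Only the specificity form with d = 0.05, prevalence 40% and two-sided z gives 327. For 327 to be the number of AF episodes needed for sensitivity, d would have to be 1.96 × √(0.95 × 0.05 / 327) = 0.024.

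**From units to patients.**
- The plan: 327 / 42 = 7.8, so 8 subjects per ICM.
- With the AF share only, and 40% of patients having episodes: 0.40 × 42 = 16.8 per patient, and 131 / 16.8 = 7.8, so again 8. The 40% cancels, so this is an identity.
- Yield of 15 patients at 40%: 0.40 × 15 × 42 = 252 AF episodes. This is below 327 but above 131 and 73.
- Yield if all 15 have episodes: 630.
- Share of patients with episodes at which 15 patients reach 327: 327 / 630 = 52%.

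**Repeated episodes.** With 42 episodes per patient and within-patient correlation ρ, the effective number is 252 / (1 + 41ρ). It stays at 73 or more up to ρ = (252/73 − 1)/41 = 0.06, and at 131 or more up to ρ = (252/131 − 1)/41 = 0.02.

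**Effect of the missing unit (illustration).** Take 252 AF episodes, sensitivity 95% and PPV 85%. Then TP = 239.4, FN = 12.6 and FP = 239.4 × 0.15 / 0.85 = 42.2. Assume 180 days of follow-up, with each episode, true or false, counted as one unit.

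| Non-AF unit | Number | Specificity | NPV |
|---|---|---|---|
| Units implied by 327 | 196 | 78.4% | 92.4% |
| Patient-days | 15 × 180 − 252 = 2,448 | 98.3% | 99.5% |
| 6-minute windows | 15 × 180 × 240 − 252 = 647,748 | 99.99% | 99.998% |

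**Effect on a difference between devices.** Compare PPV 85% with the 64% that section 5 reports for a first-generation ICM. At 64%, FP = 239.4 × 0.36 / 0.64 = 134.7, which is 92.4 more.
- On patient-days with one false episode per day: 92.4 / 2,448 = 3.8 points.
- On patient-days with five false episodes per day: 0.8 points.
- On 6-minute windows: 92.4 / 647,748 = 0.014 points.

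**The case against.** The strongest reply is that little depends on this. The study is a descriptive pilot, no test or decision rule uses specificity or NPV, and sensitivity and PPV can be formed from episodes. That stands, and it limits the severity.

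A reader might infer that 15 per ICM is too few, since 327 / 16.8 = 19.5 would mean 20 per ICM. The documents do not support this. The figure of 20 follows only if all 327 units must be AF episodes, which is the label that does not fit the formula. The 40% is also worded as a floor, for patients selected for AF burden above 2% (section 7) or for high burden or frequent episodes (section 8.4). The total of 30 was not derived from 327.

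A reader might also infer that specificity and NPV cannot be obtained from the planned data, because only electrograms that a device labels as AF are downloaded and adjudicated (sections 8.8 and 8.10.1). That goes too far. Section 8.9.1 synchronises the clocks and programs the CIED to record any AT/AF, and both devices are downloaded at 6 months. A time-based unit can be built from these data. What is missing is its definition.

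Finally, the specificity figures and the gaps between devices are illustrations. The clustering of false episodes is assumed, and the 64% belongs to an older device. They show that the unit matters, not how large a real difference would be.

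**Conclusion.** The point holds in two linked parts and should be fixed.

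First, the AF-episode requirement in section 11.1 is wrong as labelled. The 327 is a specificity-driven total of about 131 AF and 196 non-AF units, against 73 AF episodes for sensitivity. This rests on the inferred half-width of 0.05, the only value tried that returns 327. The 40% is a share of patients used as a share of units. The minimum of 8 per ICM is unchanged, and 252 AF episodes per ICM exceed 131 or 73 if episodes are independent. That margin is lost at a within-patient correlation above about 0.02 (for 131) or 0.06 (for 73).

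Second, specificity and NPV are primary measures whose values are not determined until a non-AF unit is fixed. In the illustration specificity runs from about 78% to 99.99% with the same detections. Any gap between devices also depends on the unit and on how false episodes cluster. Sensitivity and PPV do not need this unit.

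**What to change.** 1. In section 11.1, restate 327 as about 131 AF plus 196 non-AF units, or give the sensitivity-based figure of 73 AF episodes. State the half-width, the unit to which the 40% refers, and that no allowance is made for repeated episodes within a patient.
2. In sections 3, 6 and 11.2, state that sensitivity and PPV are per episode and that specificity and NPV are per patient-day. Fix this before data review. Count only days covered by retrieved logs from both devices, and report uncovered days by arm.

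Removing specificity and NPV from the primary outcome is an option, not a necessity.

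**Cost.** A text amendment, with approval under section 16.3 if it is substantial, and a day-level tabulation. No extra patients, visits or adjudication are needed. Day-level specificity can hide a false ICM episode on a day with true AF. No section describes capture of recording uptime, so days inside a retrieved log would have to be assumed recorded, and the plan should say so.
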